7.14.2 Suspension Rules

The DMC will receive rapid notification of all SAEs associated with the use of AST-OPC1 and of all reports of cyst/cavity formation. The DMC will operate under a high degree of flexibility and will tend to err on the side of protecting subjects' safety until satisfactory resolution of potential problems is obtained. Any event that triggers study suspension will be reported to the FDA and to the IRBs. If study suspension occurs, both enrollment of new subjects and administration of AST-OPC1 will be suspended.

The following events will be used as study suspension rules:

• Death or unexpected neurological deterioration, possibly related to AST-OPC1, the injection procedure used to administer AST-OPC1, and/or the concomitant immunosuppression administered

- Evidence of direct spinal cord damage related to the volume of injection
- Development of an enlarging mass or expanding ectopic tissue within the central nervous system, other than the expected filling of the lesion cavity by AST-OPC1
- Any CSF infection or inflammation that is more than a transient reaction to AST-OPC1 injection.

7.14.3 ISNCSCI Assessment Tool

The ISNCSCI was developed by the American Spinal Injury Association (ASIA) in 1982 in order to promote common definitions of neurological levels and the extent of complete injuries in patients with SCI and to achieve more consistent and reliable data among centers participating in the National Spinal Cord Injury Database. This tool is described in detail in Appendix D.

The ISNCSCI data forms will be reviewed periodically by an independent expert. The reviewer will look for inter- or intra-subject trends that may trigger a repeat examination or a DMC review.

7.14.4 MRI

General guidance on the objectives and procedures of the serial MRI scans is provided in Appendix E.

If a subject becomes pregnant, the decision to perform subsequent MRI scans will be made in consultation between the Investigator, the local radiologist, the Sponsor, and the subject. The decision about performing an MRI will be based on findings from previous MRIs, clinical findings, the risk/benefit ratio, and timing (e.g., whether the MRI can safely be postponed until the subject is no longer pregnant). If an MRI is performed on a pregnant subject, gadolinium-DTPA contrast will not be used.

7.14.5 Pain Scale

Pain assessment will be performed using the International Spinal Cord Injury Pain Basic Data Set (http://www.iscos.org.uk/international-sci-data-sets). The purpose of the Basic Data Sets is to promote uniform data collection in a standard format, with precise instructions for each question (Biering-Sørensen 2006). The Basic Data Sets are intended to be collected with information from the Core Data Set, which includes information such as:

date of birth and injury, gender, cause of spinal cord lesion and neurological status, whether surgery was performed, and whether associated injuries are present (DeVivo 2006). Three questions have been added to the Pain Basic Data Set to assess allodynia based on expert recommendation.

Baseline pain assessments will not be performed due to proximity with the original SCI and surgery. Posttreatment analyses of changes in pain over time will be exploratory in nature.

7.14.6 Spinal Cord Independence Measure

The SCIM was developed as a comprehensive rating scale specifically for persons with SCI. The instrument assesses activities of daily living, capturing the economic burden as well as the impact on a subject's overall medical condition and comfort. Reliability and validity of the SCIM Version III were recently established in a multicenter international study (Itzkovich 2007). As with pain assessment, analyses of changes in SCIM will be exploratory.

7.14.7 Assessment of Urinary Tract and Bowel Function

Assessment of lower urinary tract function and bowel function will be performed using the respective International Spinal Cord Injury Basic Data Sets (http://www.iscos.org.uk/international-sci-data-sets). Basic Data Set information for lower urinary tract function and bowel function will be collected at key posttreatment intervals to assess changes in function; analyses will be exploratory.

7.14.8 Immune Response Monitoring

As described in Section 1.3.4, no acute or chronic immune responses to AST-OPC1 have been observed to date in the previous trial. Therefore, this study will utilize a similar immunological monitoring plan, but with a slightly reduced frequency of blood sample collection at earlier time points. Donor-specific responsiveness to AST-OPC1 will be evaluated using the mixed lymphocyte reaction to monitor T cell responses (Okamura 2007) and panel reactive tests to measure AST-OPC1-specific alloantibodies. Additional assays may include cytokine and RNA changes analysis.

In addition, CSF will be collected via lumbar puncture immediately prior to AST-OPC1 injection and at study Day 60. The CSF will be tested for donor-specific responsiveness to AST-OPC1 and for evidence of inflammation, based upon total protein, IgG index, and oligoclonal bands.

8 TERMINATION

8.1 Study Completion

At the time of study completion, subjects will transition from this protocol to the long-term follow-up protocol AST-OPC1-02. Subjects will be reconsented at the time of transition.

8.2 **Premature Discontinuation from Study**

Subjects can withdraw from the trial on their own volition or be withdrawn by the Investigator at any time. If a subject who received AST-OPC1 is considering withdrawing from the study, the Investigator should discuss the implications of withdrawing and work with the subject to collect as much safety data as possible, including a final safety visit. If a subject who received AST-OPC1 voluntarily withdraws from this study, they will be nevertheless asked to participate in the long-term follow-up companion protocol AST-OPC1-02.

Specific instances that may precipitate discontinuation of individual subjects from the study are as follows:

- intercurrent illness precluding the continuation of protocol observations
- withdrawal of consent by the subject
- loss to follow-up
- death of subject

If the Investigator is unable to contact a subject for follow-up, the Investigator will attempt to contact the subject 3 times by phone. If unable to reach the subject by phone, a registered letter will be sent. If the Investigator is still unable to reach the subject, the subject will be considered lost to follow-up.

8.3 Study Discontinuation at Site

The study will be completed when all subjects who received AST-OPC1 have either completed the Day 365 visit, discontinued participation, or were lost to follow up.

The Sponsor retains the right to terminate the study at an individual institution and remove all the study materials from the study site for reasons including the following:

- completion of the study at the site
- unanticipated safety information indicating a potential and unacceptable health hazard caused by the investigational product

- significant protocol deviation or noncompliance on the part of the Investigator for reasons such as informed consent violations, other regulatory or ethical irregularities, unsatisfactory enrollment, or inaccurate data handling or reporting
- withdrawal of investigational product from research use
- termination of this study by the Sponsor

9 PLANNED ANALYSES

All analyses will be descriptive in nature. No inferential statistical tests will be conducted.

9.1 Sample Size Considerations

This trial employs a cross-sequential cohort design for Phase 1 dose escalation in cervical AIS-A and AIS-B subjects. Power calculations have not been performed, as the primary objective is to collect safety and tolerability information on a limited number of subjects per dose level and AIS grade.

9.2 Study Endpoints

The primary endpoint of this Phase 1/2a study is safety and includes observations related to AST-OPC1 tolerance, the injection procedures, and the protocol-specified immunosuppression regimen. Secondary and exploratory endpoints focus on preliminary evidence of efficacy.

9.2.1 Primary

- Incidence and severity of adverse events
- Changes in laboratory variables
- Changes at the injection site as monitored by MRI

9.2.2 Secondary

• Changes in neurologic function as assessed by the ISNCSCI

9.2.3 Exploratory

- Changes in posttreatment pain as assessed by the International Spinal Cord Injury Pain Basic Data Set
- Changes in aspects of daily living as assessed by the SCIM scale
- Changes in lower urinary tract and bowel function
- Changes in hand function on the GRASSP assessment
- Changes in volitional performance using the Spinal Cord Ability Ruler

9.3 Data Analysis Methods

For all safety and efficacy analyses, the All Treated population will be used, comprised of all subjects who received an injection of AST-OPC1. The 30-day safety data from subjects who had their DVT prophylaxis withdrawn but who never received AST-OPC1 will be assessed separately.

Conventional descriptive statistics will be used to summarize subject demography, baseline characteristics, disposition, and history. Discrete variables will be expressed with number and percentage and continuous variables with mean, standard deviation, median, and range as appropriate. Due to the small sample sizes per dose level and AIS grade planned for this study, data tabulations may be supplemented with subject narratives.

9.3.1 Safety Analyses

All reported adverse events will be coded to a preferred term and classified by System Organ Class using the current version of MedDRA. Adverse events will be listed by subject and will include preferred term, verbatim term, severity, seriousness, relationship, action taken, and outcome. Relationship will address attribution to the investigational product (AST-OPC1), the surgical procedure, and/or the immunosuppressive agent. Tabulations will be prepared for all adverse events, related events, Grade 3 and higher events, and serous events. Designated adverse events of special interest will be tabulated separately as appropriate.

Summary statistics of individual clinical laboratory parameters will be prepared by time period. Shift tables comparing baseline versus most abnormal value will be generated for selected analytes with standard toxicity grades. For selected laboratory analytes, the frequency of abnormal values and/or the incidence of Grades 3 and 4 values may be tabulated if appropriate.

Clinically significant changes in physical examination findings and ECGs will be presented descriptively. Vital signs will be summarized and listed by subject. Findings from immunological assessments will be presented appropriately.

Concomitant medications will be coded to generic term using the World Health Organization Drug Dictionary and will be tabulated across subjects and listed by subject.

9.3.2 Efficacy Analyses

Neurological function will be evaluated by characterizing upper extremity motor scores and motor level on the ISNCSCI exam (point estimate and 95% CI) by time point. The percentage of AIS-A subjects within Cohorts 2 and 3 who recover at least 2 motor levels at 180 days and at 365 days will be evaluated and compared to recent historical controls (Steeves, 2011 & 2012).

The results from the exploratory assessment tools (GRASSP, SCIM, Spinal Cord Ability Ruler, urinary tract and bowel function) will be tabulated and analyzed using statistical methods appropriate for each type of data set. Efficacy results will be presented by dose level and AIS grade, and across all subjects as appropriate.

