A key safety consideration for patients with a C4 NLI is that an ascending neurological level (i.e., to C3 or higher) could result in a loss of one's ability to breathe without the assistance of a ventilator. To date, a total of 17 subjects have received AST-OPC1 in this study, and no subject has had an ascending NLI following AST-OPC1 administration. In addition, of the 12 subjects who have reached the six-month follow up visit, 11 have improved at least one motor level on at least one side relative to baseline and 1 has a stable motor level relative to baseline. In order to provide an additional margin of safety, patients with a C4 NLI must have an UEMS \geq 1 in order to be eligible for this study and a staggering rule has been added for Cohorts 2-5 that requires a 14-day stagger between the dosing of any two consecutive subjects who have a C4 NLI.

Rationale for changing the dosing window to 21-42 days post-SCI

The current dosing window of 14-30 days was selected to avoid the early hemorrhage and inflammation that occurs following SCI, as well as the scar tissue formation that occurs in the chronic phase of SCI. This window was also based on the preclinical data available prior to the initiation of this clinical study. However, Asterias recently completed a new preclinical study to further evaluate the appropriate dosing window for AST-OPC1, and the findings from this study suggest that the optimal dosing window in human subjects may extend to at least 60 days post-SCI (see Investigator's Brochure for details).

Asterias reviewed these new preclinical data with the current study investigators and several SCI experts to determine whether the dosing window should be adjusted. Consideration was also given to the planned inclusion of patients with a C4 NLI. Based on these reviews, it was determined that a dosing window of 21-42 days post-SCI would still be squarely within the subacute period but would also allow more time for patients to be medically stable prior to undergoing elective surgery for AST-OPC1 administration.

Amendment 2: 03 May 2016

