The primary changes in this amendment were: 1) reduction of the staggering within each cohort to 8 days only between the first two subjects, 2) addition of two cohorts of subjects who are AIS-B, and 3) expansion of the acceptable age range to 18-69 years old at the time of SCI. This amendment also included several administrative changes and minor revisions to the study endpoints, inclusion/exclusion criteria, and schedule of assessments.

Amendment 1: 17 February 2015

This amendment contained a few minor administrative updates, corrected several minor typographical errors in the original protocol, and eliminated the UAB-IMR assessments. The UAB-IMR was eliminated because the clinical investigators and several expert SCI consultants noted that any clinically meaningful return of motor function in the lower extremities would be observed on both the ISNCSCI exam and the UAB-IMR exam. Thus, the latter exam was determined to be redundant for this clinical study.

Summary of changes in Amendment 3:

No.	Change	Section(s)
1	Study Objectives: Updated to reflect that the dosing window is being changed from 14-30 days post-SCI to 21-42 days post-SCI	Synopsis, Sections 2, 3.1
2	Study Population: Added an additional staggering rule for Cohorts 2-5 that requires a 14-day stagger between the dosing of any two consecutive subjects who have a C4 neurological level of injury (NLI)	Synopsis, Sections 3.1.1, 3.1.2
3	Inclusion Criteria: Expanded to include patients with a C4 neurological level of injury (NLI) if their upper extremity motor score (UEMS) is ≥ 1	Synopsis, Section 4.1
4	Inclusion Criteria: Changed the age requirement to apply at the time of consent rather than at the time of injury	Synopsis, Section 4.1
5	Inclusion Criteria: Changed the requirement for obtaining informed consent within 25 days post-SCI to within 37 days post-SCI to reflect the new dosing window	Synopsis, Section 4.1
6	Inclusion Criteria: Changed the requirement for being able to participate in an elective surgical procedure to inject AST-OPC1 to 21-42 days post-SCI to reflect the new dosing window	Synopsis, Section 4.1
7	Exclusion Criteria: Added an exclusion criterion for acute, symptomatic pulmonary embolism that would create an unacceptable risk for surgery based on a recommendation from the Data Monitoring Committee and after consultation with the lead neurosurgeon for the study	Synopsis, Section 4.2
8	Duration of Treatment: Updated to reflect the new dosing window	Synopsis

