The advantages of conducting clinical trials in patients with severe cervical SCI were recently reported by Steeves et al. (2011, 2012) together with the Spinal Cord Outcomes Partnership Endeavor (SCOPE). These studies analyzed several large SCI databases and found that only 21% and 26% of people living with C4-C7 cervical AIS-A spinal cord injury recovered \geq 2 upper extremity motor levels at 24 and 48 weeks after injury, respectively. These studies further showed that a \geq 2 level improvement in motor score led to a statistically significant increase in the Spinal Cord Independence Measure (SCIM) self-care subscore, suggestive of a measurable association between improvement in neurological function and a clinically meaningful functional outcome. The SCIM will also be used as an exploratory endpoint on its own since recent studies have shown that AIS-A and AIS-B patients exhibit a similar degree of recovery on the SCIM with current standard of care (Curt 2008).

Additional new outcome measures and endpoints will be explored that can further elucidate recovery of function across both complete and incomplete cervical SCI patients. One of these measures is the Graded Redefined Assessment of Strength, Sensibility, and Prehension (GRASSP). It has been shown that a baseline GRASSP exam conducted at 1 month post-SCI can predict upper limb function and self-care ability at 6 and 12 months post-SCI (Velstra 2014). Another new exploratory endpoint that will be utilized is the Spinal Cord Ability Ruler, which is a quantitative linear measure of volitional performance inclusive of all subjects in the study population (Reed, submitted). The Spinal Cord Ability Ruler is derived from the ISNCSCI and SCIM assessments.

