4.1 Inclusion Criteria

- 1. Sensorimotor complete, traumatic SCI (ASIA Impairment Scale A) for Cohorts 1, 2, and 3
- 2. Sensorimotor incomplete, traumatic SCI (ASIA Impairment Scale B) for Cohorts 4 and 5
- ISNCSCI Neurological Level of Injury (NLI) from C-5 to C-7 or a C4 NLI with an upper extremity motor score (UEMS) ≥ 1
- 4. From 18 through 69 years of age at time of consent
- 5. Single spinal cord lesion on a post-stabilization magnetic resonance imaging (MRI) scan, with sufficient visualization of the spinal cord injury epicenter and lesion margins to enable post-injection safety monitoring
- 6. Informed consent for this protocol and the companion long term follow-up protocol must be provided and documented (i.e., signed informed consent forms) no later than 37 days following injury
- 7. Able to participate in an elective surgical procedure to inject AST-OPC1 21-42 days following SCI

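### The historical rate for a two-motor-level gain describes C4-C7 injuries, while the trial admitted C4 only late and only with some arm function, so the planned comparison is not level-matched and may be biased in an unknown direction and by an unknown amount

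*Protocol*

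**What the plan says.** **The comparison.** Protocol 9.3.2 takes "The percentage of AIS-A subjects within Cohorts 2 and 3 who recover at least 2 motor levels at 180 days and at 365 days", which "will be evaluated and compared to recent historical controls"; the controls are those of two cited database reports. It states no restriction, matching or weighting of the controls.

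**The benchmark.** Protocol 1.3.1 reports that those studies "found that only 21% and 26% of people living with C4-C7 cervical AIS-A spinal cord injury recovered" at least two upper extremity motor levels, at 24 and 48 weeks after injury respectively. It gives no UEMS condition, no numerators or denominators, and no rates by level.

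**Eligibility.** Protocol 4.1 requires "ISNCSCI Neurological Level of Injury (NLI) from C-5 to C-7 or a C4 NLI with an upper extremity motor score (UEMS) ≥ 1". The Amendment 3 change table shows that the C4 part was new: "Expanded to include patients with a C4 neurological level of injury (NLI) if their upper extremity motor score (UEMS) is" at least 1. The rationale in the Summary of Amendments adds: "To date, a total of 17 subjects have received AST-OPC1 in this study".

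**The SAP.** Section 2 gives the SAP precedence over the protocol's statistical section where they differ. Section 5.1 uses Cohorts 2-5, aggregated, for all efficacy analyses. Section 5.5 rules out subgroup analyses. Section 6.3.1 tabulates the percentage gaining two or more motor levels but names no historical comparator, and Appendix 9.1 lists no table for one.

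**The concern.** The trial has no concurrent control, and this is its only external reference for efficacy. A benchmark is useful only if its patients could have been in the trial. Here C4 injuries fall within the benchmark description but were ineligible for part of the enrolment of Cohorts 2 and 3. C4 with UEMS 0 falls within the description and was never eligible.

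If two-level recovery depends on where a patient starts, a response above or below 21%/26% may partly reflect who was admitted rather than AST-OPC1. Dependence on starting level is plausible from the scale alone. The upper-limb key muscles run from C5 to T1, so a C7 motor level has only C8 and T1 left below it, while a C4 level has all five. That does not show which starting level gains two levels more often.

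**Working it through.** **Step 1. Reproduce the stated counts.** SAP 3.2.1 gives final cohorts of 3, 6, 6, 6 and 4: 3 + 6 + 6 + 6 + 4 = 25, as stated. The compared group is Cohorts 2 and 3: 6 + 6 = 12. The 21% and 26% cannot be reproduced because no counts are given.

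**Step 2. How many of the 12 were dosed before C4 was eligible?** The Amendment 3 text puts 17 subjects dosed by then but does not split them by cohort.

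- *Cohort sizes only.* Place as many of the 17 as possible outside Cohorts 2 and 3: 17 - 3 - 6 - 4 = 4. So at least 4 of 12.
- *Adding the advancement rules in protocol 3.1.2.* If anyone in Cohort 5 was among the 17, Cohort 3 had at least 2 dosed, and Cohort 3 could open only with at least 5 in Cohort 2, giving at least 5 + 2 = 7. If no one in Cohort 5 was among them, Cohorts 2 and 3 hold at least 17 - 3 - 6 = 8. So at least 7 of 12 (58%). A full enumeration gives 7 to 12. The minimum occurs, for example, at 3 + 5 + 2 + 5 + 2 = 17.

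Under the advancement rules, then, at most 12 - 7 = 5 of the 12 could have entered with a C4 NLI.

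**Step 3. Illustrate the size.** Neither document gives recovery by level, the level mix of the benchmark, or the level mix of the 12. The inputs below are therefore assumptions:

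- *s*, the C4 share of the benchmark: 20% to 50%.
- *k*, the C4 response rate relative to C5-C7: 0.5 to 2. The same *k* is used for all C4 patients, with or without arm function.

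If the pooled rate is *p*, the implied C5-C7 rate is r = p / (1 - s + s·k). If *m* of the 12 are C4, the matched rate is r × [(12 - m) + m·k] / 12.

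With p = 26%:

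| s | k | r (m = 0) | Matched rate (m = 5) |
|---|---|---|---|
| 0.2 | 0.5 | 0.26/0.90 = 28.9% | 28.9% × 9.5/12 = 22.9% |
| 0.5 | 0.5 | 0.26/0.75 = 34.7% | 34.7% × 9.5/12 = 27.4% |
| 0.2 | 2 | 0.26/1.20 = 21.7% | 21.7% × 17/12 = 30.7% |
| 0.5 | 2 | 0.26/1.50 = 17.3% | 17.3% × 17/12 = 24.6% |

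The counterpart of 26% is thus 17%-35% if none of the 12 is C4, and about 23%-31% if 5 are. With m = 0, the expected responders among 12 are 12 × 0.173 = 2.1 to 12 × 0.347 = 4.2, against 12 × 0.26 = 3.1 at the unmatched rate. For p = 21% and m = 0, the range is 0.21/1.50 = 14% to 0.21/0.75 = 28%.

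With m = 0, k below 1 puts the matched rate above 26%, so the unmatched comparison flatters the product; k above 1 does the reverse. With m = 5, the sign also depends on whether 5/12 (42%) is above or below the benchmark's C4 share.

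**Step 4. Precision.** With n = 12, a result of 3/12 has an exact 95% confidence interval of 5.5% to 57.2%.

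**The case against.** Several points on the other side stand in whole or in part.

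- *Bias is not demonstrated.* A reader might infer that the comparison is biased, or biased in the product's favour. That needs both a difference in recovery by level and a difference in level mix, and the documents supply neither. This objection stands.
- *Section 9.3.2 does not name 21%, 26% or C4-C7.* It cites the reports and leaves the control subset open, so a level-matched subset is not ruled out. This stands. But the pooled rates are the only figures the protocol gives, and the subset should not be chosen after results are known.
- *The comparison may never be run.* The SAP takes precedence, pools AIS-A with AIS-B and names no historical comparator. This stands and has to be settled first. The SAP is silent rather than explicit about dropping the comparison, however, and it keeps a two-level responder percentage that a reader could set against 21%/26%.
- *A reader might take it as certain that most of the 12 were dosed before C4 was eligible.* Cohort counts guarantee only 4. The figure of 7 assumes that the current advancement rules governed all earlier dosing, and Amendment 2 added the AIS-B cohorts.
- *NLI and motor level differ.* Under Appendix D, NLI is the most cephalad of the sensory and motor levels, so a C4 NLI can accompany a lower motor level. Section 1.3.1 does not say which level defines C4-C7. This stands, and the remedy must name the level it uses.
- *All analyses are descriptive and 12 subjects give wide intervals.* True, but an interval around the trial's response does not reveal that the reference rate comes from a different population.

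**Conclusion.** The concern holds in limited form. The benchmark is described as C4-C7. C4 was ineligible when at least 4 of the 12 compared subjects were dosed (at least 7 if the current advancement rules applied throughout), and C4 with UEMS 0 was never eligible. Protocol 9.3.2 provides no adjustment. The comparison is therefore not level-matched and may be biased, with direction and size unknown.

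The 17%-35% and 23%-31% ranges show what could happen under stated assumptions; they do not estimate what did. The wider range applies only if none of the 12 is C4. This point is separate from the difference in time origin: the historical times run from injury, the trial's from injection.

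**What to change.** 1. Reconcile protocol 9.3.2 with SAP 5.1, 5.5 and 6.3.1, and state whether the historical comparison is kept.
2. If it is kept, restrict the controls to the trial's eligibility: NLI C5-C7, or C4 with UEMS at least 1. Standardise the historical rate to the starting motor levels of the 12 subjects. Tabulate those levels and give the response with an exact 95% confidence interval. SAP 6.1.3 does not list starting level among the baseline characteristics, but the ISNCSCI data are already collected and listed.
3. If level-specific rates cannot be obtained, show the trial response by baseline motor level and label 21%/26% as unmatched context, with no statement that the trial exceeds or falls below it.

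The cost is wording in the protocol and SAP, one data request to the holders of the historical data, and a less precise benchmark because it rests on fewer controls. Nothing changes for subjects.
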